Pioglitazone for Idiopathic Gastroparesis NCT04300127 8/24/2020

Clinical Protocol Synopsis- Pioglitazone for the Treatment of Gastroparesis

Title

Pioglitazone for the Treatment of Idiopathic Gastroparesis (PIOGAS Study)

Type of study

• Open label pilot study

Objective

- The principal objective of this pilot study will be to evaluate whether 8 weeks of treatment of pioglitazone will improve symptoms as measured by the Gastrointestinal Symptom Index Daily Diary (GCSI-DD) in patients with Idiopathic Gastroparesis
- Secondary objectives of this study include:
 - To determine the effects of pioglitazone on other symptoms associated with gastroparesis using the Patient Assessment of Upper Gastrointestinal Symptom Severity Index (PAGI-SYM) and the Gastrointestinal Symptom Rating Scale (GSRS),
 - To determine the effects of pioglitazone on gastric emptying as measured by the ¹³C- Spirulina breath test,
 - To determine the effects of pioglitazone on satiety as measured by a liquid caloric test
 - To determine the effects of pioglitazone on depression and anxiety using the Beck Depression Inventory and State-Trait Anxiety Scores,
 - To determine the effects of pioglitazone on Quality of Life using the PAGI-QoL and SF-36 questionnaire,
 - To determine the effects of pioglitazone on markers of inflammation (CRP and ESR) and serum cytokine levels
 - And to determine the nature and incidence of adverse effects from a 12-week course of pioglitazone.

Treatment group

• Pioglitazone (30 mg po qd)

Population

 Age 18 years or older at registration with nausea, vomiting, and other symptoms suggestive of patients with chronic nausea and vomiting of presumed gastric origin, with symptomatic gastroparesis.

Study duration

- Up to 4 weeks of screening prior to pioglitazone treatment
- 8 weeks of treatment starting at initial dose of pioglitazone
- **4 weeks** of washout period
- Length of recruitment: 16 months

Sample size justification

- Total of **20 patients**
- Primary comparison: Baseline PAGI-SYM score versus 4, 8, and 12 weeks.

Number of clinical centers

- Johns Hopkins Bayview Medical Center.
- Mayo Clinic Scottsdale, Arizona This site will not perform enrollment of patients, It will only intervene as data analysis center under the supervision of [name].
- •

Inclusion criteria

- Age 18 years or older at registration

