- (3) Inflammatory Markers
 - CRP and ESR
- (4) Mood and Behavior
 - Beck Depression Inventory
 - State-Trait Anxiety
- (5) Adverse Events
 - Biochemical tests
 - Symptoms of cardiac or pulmonary disease
 - Any other AE reported or noted throughout the study and follow-up

Justification of sample size

This will be a pilot study recruiting 20 candidates.

Statistical analysis

All analyses will be on an intention-to-treat basis. Patients who do not have any of the decline of 1 or more in the total GCSI score recorded during the period of treatment will be counted as not improved (i.e., 0) for the primary outcome. Comparisons will also be made with baseline total GCSI score and other secondary outcomes. Numerical changes will be analyzed by descriptively comparing the between-treatment group differences in mean and median changes; P-values will be derived from Wilcoxon rank sum tests for comparison of the distribution of changes in each group The two-sided P-values so derived will be reported in the primary results paper of the trial. A two-sided P-value of 0.05 will be considered statistically significant.

Standard treatment recommendations

During the screening period, patients will receive a standardized set of recommendations to include dietary modification. The patient's medications are reviewed to eliminate drugs that might exacerbate the underlying dysmotility disorder or prevent the beneficial actions of a prokinetic agent. Dietary modification and use of pain medications as appropriate are the primary management approaches. If symptoms require further treatment during the trial, patients will be instructed to take rescue medications that they would usually take such as prochlorperazine for nausea and vomiting, and tramadol for abdominal pain. These recommendations have been prepared by the GpCRC Steering Committee as standard of care in the management of patients with gastroparesis or related disorders. This will help ensure that the patients in both treatment groups receive standard of care treatment.

Visit schedule

- Screening: at least 1 visit separated by at least 1 calendar day prior pioglitazone treatment; screening period can last no more than 4 weeks after registration
- Final pre-treatment interview, dispensing of study agent
- Follow-up visits: every 4 weeks after pioglitazone treatment throughout the 12 week study
- Post-treatment: follow-up at **16 weeks**

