(1) Screening visits and baseline data collection

Many of the PIOGAS participants will come from the patient rosters of the study physicians. Patients who appear to be eligible after chart review and completion of standard of care tests and procedures for gastroparesis will be invited to undergo screening for the PIOGAS trial. Patients considered by the clinical center investigator as likely to be eligible for participation in the APRON trial may be consented, registered and screened at a visit that is part of the ongoing clinical care of the patient.

In order to minimize the need for research-only in-person visits, telemedicine visits may be substituted for in person clinical trial visits or portions of clinical trial visits where determined to be appropriate and where determined by the investigator not to increase the participants risks. Prior to initiating telemedicine for study visits the study team will explain to the participant, what a telemedicine visit entails and confirm that the study participant is in agreement and able to proceed with this method. Telemedicine acknowledgement will be obtained in accordance with the Guidance for Use of Telemedicine in Research. In the event telemedicine is not deemed feasible, the study visit will proceed as an in-person visit. Telemedicine visits will be conducted using HIPAA compliant method approved by the Health System and within licensing restrictions.

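### The drug course is 8 weeks in the principal objective and 12 weeks in the safety objective; on the better-supported 8-week reading, mood, quality of life, weight, vital signs and exam are never scheduled on drug

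*Combined protocol and SAP*

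**What the plan says.** All of this is current text in the Combined protocol and SAP.

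- **Objective, principal:** to "evaluate whether 8 weeks of treatment of pioglitazone will improve symptoms".
- **Study duration:** 8 weeks "of treatment starting at initial dose of pioglitazone", then 4 weeks "of washout period".
- **Objective, last secondary item:** to "determine the nature and incidence of adverse effects from a 12-week course of pioglitazone".
- **Sample size justification:** the primary comparison is "Baseline PAGI-SYM score versus 4, 8, and 12 weeks".
- **Visit schedule:** visits every 4 weeks "after pioglitazone treatment throughout the" 12-week study, then "Post-treatment: follow-up at" 16 weeks.
- **Statistical analysis:** a patient with no qualifying GCSI fall within the treatment period counts as not improved.
- **Treatment Start Visit and Follow-up visits:** time zero is the first day of treatment. The CBC, metabolic panel, CRP and ESR are repeated only at week 8. GSRS, SF-36v2, BDI-II, STAI, the physical exam, weight and vital signs are repeated only at week 12. PAGI-SYM and PROMIS are taken, and GCSI-DD diaries collected, at weeks 4, 8 and 12. Week 16 has history, side effects and global questions only.

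**The concern.** The length of the drug course decides which measurements are on-treatment values, and the plan gives two lengths. Three things depend on it.

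First, the primary outcome. The responder rule refers to the treatment period, so a patient whose qualifying GCSI fall first appears in weeks 9 to 12 is a responder if the course is 12 weeks and a non-responder if it is 8.

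Second, the secondary objectives on depression, anxiety and quality of life ask for the effects of pioglitazone. If dosing stops at week 8, the instruments behind them are completed before the drug and again at the end of washout, never during it. A null result could then mean no effect or an effect that had faded. SF-36v2 is the only quality-of-life instrument that appears in the visit schedule, so no other scheduled measure fills that gap.

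Third, safety. The Risks section lists weight gain and swelling. On the 8-week reading no weight, vital signs or exam is scheduled while patients take the drug.

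**Working it through.** **Step 1. Which length?** Setting the sections side by side:

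- For 8 weeks: the principal objective; Study duration, which is the section that defines the length; the 4-week washout, since 8 + 4 = 12 matches the 12-week study in Visit schedule; and the laboratory repeat at week 8.
- For 12 weeks: the safety objective; and the post-treatment visit, since 12 + 4 = 16.
- Neutral: the adherence review at week 12 (the same sentence appears at weeks 4, 8 and 12); the primary comparison running to week 12 (it could follow symptoms through washout); and the fuller week-12 assessment (it could be an end-of-study visit).

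Eight weeks is better supported. The week-16 visit is the one item in the schedule that points the other way.

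**Step 2. Assessment timing under each reading.** Inputs are the visit weeks in Follow-up visits, counted from the start of treatment. The visit text and the data collection table agree on these items.

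| Measure (post-baseline weeks) | 8-week course | 12-week course |
|---|---|---|
| GSRS, SF-36v2, BDI-II, STAI, weight, vital signs, exam (12) | 0 of 1 on drug; 12 − 8 = 4 weeks after last dose | 1 of 1; 12 − 12 = 0, at end of treatment |
| CBC, CMP, CRP, ESR (8) | 1 of 1, at end of treatment | 1 of 1, but 12 − 8 = 4 weeks before the end; 8/12 = 67% of the course |
| PAGI-SYM, PROMIS (4, 8, 12) | 2 of 3 on drug | 3 of 3 on drug |

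Neither reading puts the full set of measures at the last week of treatment.

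**Step 3. Week 12 in the primary comparison.** PAGI-SYM has a 2-week recall. At week 12 it covers weeks 12 − 2 = 10 to 12. With dosing ended at week 8, that window lies wholly in washout, whereas the week-8 value covers weeks 6 to 8 and is wholly on drug.

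**Step 4. Responder window.** 8 or 12 weeks, and 12/8 = 1.5-fold. With 20 patients, each patient whose classification changes moves the responder proportion by 1/20 = 5 percentage points. The documents give nothing from which to estimate how many would change.

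**The case against.** The strongest reply is that this is a wording slip with limited consequences. Eight weeks stands in the two places that matter most. The synopsis carries text that does not fit this study (a reference to the APRON trial, and to both treatment groups in a single-arm design), so the 12-week phrase and the week-16 visit, which has no column in the data collection table, may be leftovers. The affected measures are secondary, in a 20-patient open-label pilot where even an on-drug change could not be firmly attributed to pioglitazone.

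Much of this stands. It supports reading the course as 8 weeks and keeps the point short of a threat to the main symptom data. It does not remove the point: correcting the wording to 8 weeks is exactly what leaves the four questionnaires, weight, vital signs and exam off drug. No objective concerns persistence after stopping, so a deliberate test of durability is not a documented explanation.

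A reader might infer more than the documents support:

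- *That supply must be fixed on day one, because dispensing is marked once.* Treatment Start Visit allows the pharmacy to deliver drug to the home, so later supply is not excluded.
- *That the missing values are lost for good.* An amendment can add them for every patient not yet past week 8.
- *That the two lengths are evenly supported, with the week-12 adherence review as evidence for 12.* Step 1 shows otherwise.
- *That adverse-event history falls short because weeks 12 and 16 are off drug.* Reviews at weeks 4 and 8 cover the whole 8-week exposure; the later ones are ordinary follow-up.
- *That washout values will be reported as drug effects.* The plan does not say how week-12 values will be labelled. The problem is that it does not label them.

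**Conclusion.** The contradiction is certain; that 8 weeks is the intended length is the better-supported reading, not a proven one. On that reading, GSRS, SF-36v2, BDI-II, STAI, weight, vital signs and exam have 0 of 1 post-baseline measurements on drug, and the single value falls 4 weeks after the last dose. Losing an on-drug GSRS matters least, because PAGI-SYM and PROMIS cover gastrointestinal symptoms at weeks 4 and 8. The gaps that matter are depression, anxiety, quality of life and the physical check for weight gain and swelling. The primary responder window is open between 8 and 12 weeks.

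The symptom diaries, laboratory tests and reported adverse events on drug are unaffected. The conclusion assumes dosing stops at week 8 as Study duration states; it assumes no effect size and no rate at which an effect fades. It should be fixed, but it does not undermine the collection of the primary symptom data.

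**What to change.** State 8 weeks of treatment throughout and correct the 12-week wording in the safety objective. Reconcile the week-16 visit: either remove it or describe it as further follow-up, 16 − 8 = 8 weeks after the last dose. Define the responder window as weeks 0 to 8. Add GSRS, SF-36v2, BDI-II, STAI, weight, vital signs and physical exam at the existing week-8 visit, beside the laboratory tests already there. Label week-12 values as washout in the analysis, including in the primary comparison line.

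If the sponsor intended 12 weeks, correct the principal objective and Study duration instead, define the responder window as weeks 0 to 12, and repeat CBC, CMP, CRP and ESR at week 12. The Risks section lists decreased hemoglobin and raised liver enzymes, and no laboratory test is otherwise planned in the last 4 weeks of dosing.

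The cost is an amendment and a longer week-8 visit. That visit must be in person for the exam, although the plan says "telemedicine visits may be substituted for in person clinical trial visits" where appropriate; the questionnaires can be completed through REDCap. Keeping the four questionnaires at week 12 as well, to describe washout, adds some patient burden. Under the 12-week option the cost is one blood draw at an existing visit.

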- Diagnosis of gastroparesis as documented by gastric emptying scintigraphy (4-hour emptying after a low-fat meal with any combination of 2 and 4 hour retention of >60% and 10% respectively)
- Ongoing symptoms referable to gastroparesis (i.e. nausea and vomiting, bloating, and abdominal pain)
- Exclusion of other causes of symptoms such as mechanical gastrointestinal obstruction, uncontrolled esophagitis, peptic ulcer disease, etc. by standard radiographic or endoscopic tests
- Females will be required to use adequate contraceptive methods during study participation as determined by the Principal Investigator and the study team members

Exclusion criteria

- Another active disorder which could explain symptoms in the opinion of the investigator
- Age < than 18 years
- Pregnancy or nursing
- Previous surgery of the upper gastrointestinal tract including vagotomy
- Another active disorder which could explain symptoms in the opinion of the investigator
- Use of narcotics more than 3 days per week
- Significant hepatic injury as defined by significant alanine aminotransferase (ALT) and aspartate aminotransferase (AST) elevations of greater than 2xULN or a Child-Pugh score of 10 or greater
- Serious systemic disease, such as recent myocardial infarction/unstable angina, decompensated congestive heart failure, severe pulmonary disease with dyspnea at rest, or altered mental status from any cause
- Diabetes as defined by HbA1c >6.5 and/or fasting blood sugar of >125 mg/dL
- Contraindications to pioglitazone such as hypersensitivity or allergy
- Concurrent use of: estradiol, ethynyl estradiol, mestranol, pazopanib, warfarin, digoxin, atorvastatin, ranitidine, gemfibrozil, fexofenadine, midazolam
- Any other condition, which in the opinion of the investigator would impede compliance or hinder completion of the study
- History of bladder cancer or family history of bladder cancer
- Failure to give informed consent

Outcome measures

- **Primary:** The primary outcome measure is a binary (0,1) variable indicating improvement as measured by a decline of 1 or more in the total GCSI score
- Secondary outcome measures will be defined to address the following areas:
 - (1) Gastrointestinal symptoms
 - Subscores for the GCSI: nausea/vomiting, postprandial fullness, bloating
 - Total and Subscores for the GSRS
 NIH Patient Reported Outcome Measurement Information System (PROMIS)

gastrointestinal symptom scales.

- (2) Quality of Life
 - PAGI-QoL
 - SF-36

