- Patient Assessment of Upper Gastrointestinal Disorders-Quality of Life (PAGI-QoL): A validated 30 item questionnaire to assess quality of life in patients with dyspepsia, GERD, or gastroparesis. Copyright© 2004 Johnson & Johnson.
- State Trait Anxiety Inventory: The STAI is a 40-item self-report measure designed to assess both situational and characterological anxiety. This measure provides two subscale scores (State and Trait) and has been shown to exhibit good reliability and internal consistency.
- Beck Depression Inventory, Second Edition (BDI-II): The BDI-II is a commonly used, reliable 21-item self-report measure designated to assess for depression.

- Patient Assessment of Upper Gastrointestinal Disorders-Symptoms (PAGI-SYM): The self-reported questionnaire is composed of 20 items and 6 subscales. The severity of each symptom item over a 2-week recall period is scored from 0 (none or absent) to 5 (very severe). The GCSI, a 9-symptom survey relevant to gastroparesis stratified in 3 subscales – nausea/vomiting, fullness/early satiety, and bloating, is contained in the PAGI-SYM. The GCSI correlates with patient severity ratings and is responsive to changes in overall symptoms. Two additional items for constipation and diarrhea also will be recorded and scored and their main symptom will be determined.
- Gastrointestinal Symptom Rating Scale (GSRS): The GSRS is a disease-specific instrument of 15 items combined into five symptom clusters depicting Reflux, Abdominal pain, Indigestion, Diarrhea, and Constipation. The GSRS has a seven-point graded Likerttype scale where 1 represents absence of troublesome symptoms and 7 represents very troublesome symptoms. The reliability and validity of the GSRS are well-documented and norm values for a general population are available.
- PROMIS NIH Scale: The Patient-Reported Outcomes Measurement Information System (PROMIS®) GI Symptom item bank captures upper and lower GI symptoms (reflux, disrupted swallowing, nausea/vomiting, belly pain, gas /bloating /flatulence, diarrhea, constipation, and fecal incontinence).

Recruitment Procedures

Individuals Responsible for Approaching Participants:

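### The primary endpoint is stated in conflicting ways, and the responder definition leaves its source, scoring and time window open

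*Combined protocol and SAP*

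**What the plan says.** Four places in the synopsis bear on the primary endpoint.

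- **Objective.** The principal objective is to learn "whether 8 weeks of treatment of pioglitazone will improve symptoms as measured by the Gastrointestinal Symptom Index Daily Diary (GCSI-DD". PAGI-SYM appears in the secondary list: "To determine the effects of pioglitazone on other symptoms associated with gastroparesis using the Patient Assessment of Upper Gastrointestinal Symptom Severity Index (PAGI-SYM".
- **Sample size justification.** "Primary comparison: Baseline PAGI-SYM score versus 4, 8, and 12 weeks".
- **Outcome measures.** The primary outcome is "a binary (0,1) variable indicating improvement as measured by a decline of 1 or more in the total GCSI score". The secondary list includes "Subscores for the GCSI: nausea/vomiting, postprandial fullness, bloating" but does not name the PAGI-SYM.
- **Statistical analysis.** Patients without "any of the decline of 1 or more in the total GCSI score recorded during the period of treatment" are scored as not improved.

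Two instruments can yield a GCSI. One is the nightly GCSI-DD, issued at the screening, treatment start, week 4 and week 8 visits. The other is the PAGI-SYM, completed at screening and at weeks 4, 8 and 12. Under Specific Tests and Questionnaires, the PAGI-SYM entry says "The severity of each symptom item over a 2-week recall period is scored from 0 (none or absent) to 5 (very severe", and describes "The GCSI, a 9-symptom survey relevant to gastroparesis stratified in 3 subscales" as part of that questionnaire. It gives no rule for forming a total. The GCSI-DD has no entry in that section.

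Treatment length is stated as 8 weeks, followed by 4 weeks of washout, in Study duration. The adverse-effects objective refers to a 12-week course. The Visit schedule places post-treatment follow-up at week 16, and the week 12 visit still reviews study drug adherence.

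**The concern.** The statements differ in instrument (diary or questionnaire), in type of variable (a score compared at three times or a binary response) and in timing (week 8; weeks 4, 8 and 12; or any time on treatment). Nothing in the document ranks or reconciles them.

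This is an open-label study of one group of 20, so the response rate is its main result. The plan also sets a two-sided 0.05 level and foresees a primary results paper. Two analysts who follow the text faithfully could report different primary results from the same data, and the choice between versions could be made after the results are known.

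**Working it through.** **1. The plan's own figure.** The sample size of 20 cannot be reproduced, because no effect size, SD, response rate or power is given. It is presented as a pilot number, so there is nothing to check it against.

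**2. Scale (item data from the PAGI-SYM entry).** Nine items scored 0 to 5.

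- Sum: range 0 to 9 × 5 = 45. A fall of 1 is 1/45 = 2.2% of the range, which is one item of nine falling one grade.
- Item mean: range 0 to 5. A fall of 1 is 1/5 = 20% of the range, or 9 points on the sum.

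The same threshold therefore differs ninefold in meaning. A mean of the three subscale means would also run from 0 to 5.

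**3. Number of readings in an any-time rule.**

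- PAGI-SYM source: two on-treatment visits (weeks 4 and 8) for an 8-week course, three (adding week 12) for a 12-week course.
- Diary source: three weeks of diary are supplied at treatment start and four at the week 4 visit, so 3 + 4 = 7 weekly means up to week 8. No rule for averaging nights is given, so weekly means are themselves an assumption.

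**4. Illustrative response rates with no average change.** The documents give no SDs or correlations, so all variability inputs here are assumed. The change from baseline at each reading is Normal(0, SD), with equal correlation ρ between readings. The 0-5 scale, documented only for the GCSI inside the PAGI-SYM, is assumed to hold for the diary too.

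- One reading: Φ(−1/SD).
- Any of k readings: 1 − ∫ φ(u) [Φ((1/SD − √ρ·u)/√(1−ρ))]^k du.

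| 0-5 mean | one reading | either of two | any of seven |
|---|---|---|---|
| SD 1.0, ρ 0.7 | 15.9% | 23.3% | 38.6% |
| SD 0.5, ρ 0.7 | 2.3% | 3.8% | 8.2% |
| lowest in grid (SD 0.5, ρ 0.9) | 2.3% | 3.2% | 5.2% |
| highest in grid (SD 1.2, ρ 0.5) | 20.2% | 31.6% | 55.5% |

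For three readings with SD 1.0 and ρ 0.7, the same formula gives 28.2%.

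**5. Sum scoring at one reading.** Multiply the SD by 9. A sum moves in whole points, so a fall of at least 1 is taken as crossing 0.5.

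- SD 0.5 × 9 = 4.5: Φ(−0.5/4.5) = 45.6%.
- SD 1.0 × 9 = 9: Φ(−0.5/9) = 47.8%.
- SD 1.2 × 9 = 10.8: Φ(−0.5/10.8) = 48.2%.

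**6. In patients.** With SD 1.0 and ρ 0.7, 20 patients give 20 × 0.159 = 3.2 expected responders at one reading and 20 × 0.386 = 7.7 at any of seven. Exact 95% intervals are 3.2% to 37.9% for 3 of 20 and 19.1% to 63.9% for 8 of 20.

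**The case against.** The best defence is that the two sections which define the primary outcome agree with each other: both use a binary fall of at least 1 in total GCSI. The GCSI sits inside the PAGI-SYM, so the sample-size line may be loose labelling. The PAGI-SYM is scheduled at exactly the weeks that line names, and the GCSI subscores in the secondary list match its subscales. A reader might therefore infer three unrelated endpoints, and that would go too far. Still, loose labelling would point to the questionnaire while the objective points to the diary, and a score compared at three times is not a binary response.

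A reader might also infer that no time rule exists. Read literally, the Statistical analysis section does give one: any recorded fall during treatment counts. What it lacks is a settled window length and, for the diary, an averaging rule. Preferring a fixed visit over an any-time rule is a design preference, not the correction of an error.

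Three further inferences are not supported.

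- The sum reading should not be taken as the likely one, since a one-grade change in one item is an improbable meaning of improvement. The text is simply silent.
- The documents do not show that the wording was left loose in order to choose later.
- They contain no go/no-go rule and mention no larger trial, so no consequence for a later study can be claimed.

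Finally, counting natural change as response comes from the uncontrolled design. A week 8 endpoint reduces the number of chances but does not remove the problem.

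**Conclusion.** The point holds as a contradiction in the trial's main result and must be fixed before analysis. The conflict in instrument, variable type and timing is in the text and needs no assumption. The ninefold scale difference follows from the nine 0-5 items, if the total is either a plain sum or a mean. An any-time rule can never give fewer responders than any one of its own readings.

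The sizes are illustrative. At an assumed SD of change of 1.0 and correlation of 0.7, with no average change, the rate is about 16% at one reading, 23% at either of two visits and 39% at any of seven weekly diary means. The 39% applies only if the diary is the source and shares the 0-5 scale. The 46-48% for an integer sum at one reading covers SDs of change of 0.5 to 1.2 on the mean scale. The direction is secure; the magnitudes depend on the assumed inputs.

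**What to change.** Name one primary endpoint and state it identically in the Objective, Sample size, Outcome measures and Statistical analysis sections, with its source, scoring, time point and handling of missing data.

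The option closest to the stated objective is a fall of at least 1 in the GCSI-DD total, scored as an item mean, from the mean of the one-week screening diary to the mean of the last 7 nights before the week 8 visit. Set a minimum number of completed nights for each mean, and count patients without an evaluable week 8 mean as not improved. Add a GCSI-DD entry, with item count and range, to the instrument section. Say openly that this replaces the any-time wording: a patient with a fall at week 4 and no week 8 data could count as improved under the present text but would not here.

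If the sponsor intends the PAGI-SYM GCSI or an any-time response, name that instead, list its readings, and make the other versions secondary. In either case, delete the PAGI-SYM primary-comparison line or relabel it as secondary, and report the proportion with an exact 95% confidence interval.

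The sponsor must reconcile the 8-week and 12-week treatment statements before fixing the time point, and so that week 12 can be labelled as on or off drug.

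The cost is document wording; no new visit or form is needed, because the screening diary and the diary collected at week 8 supply both means. The downsides of the week 8 diary option are a lower response rate than under an any-time rule (about 16% against 39% in the illustration) and a baseline diary that may precede the first dose by up to about 4 weeks.

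### The primary outcome reduces the GCSI change to yes/no in 20 patients, losing at least about 36% of the information under normality, and the numeric analysis kept beside it needs a second group

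*Combined protocol and SAP*

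**What the plan says.** Under Outcome measures the only primary outcome is defined thus: "The primary outcome measure is a binary (0,1) variable indicating improvement", where improvement means that the total GCSI falls by at least 1 point. Under Statistical analysis, patients with no such decline "recorded during the period of treatment will be counted as not improved (i.e., 0) for the primary outcome". No time point is named beyond the treatment period.

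The principal objective is to "evaluate whether 8 weeks of treatment of pioglitazone will improve symptoms", measured with the daily diary form of the GCSI. On size, the plan says only "This will be a pilot study recruiting 20 candidates", and the type of study is "Open label pilot study". The Treatment group section lists pioglitazone alone.

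The numeric score is not dropped. Statistical analysis adds: "Comparisons will also be made with baseline total GCSI score". It then describes mean and median changes compared between treatment groups, with P-values from Wilcoxon rank sum tests, and states: "A two-sided P-value of 0.05 will be considered statistically significant". Separately, the Sample size justification section labels a different analysis the primary comparison: baseline PAGI-SYM score against the scores at weeks 4, 8 and 12.

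**The concern.** The binary rule treats a decline of 0.9 like no change at all, and a decline of 3 like a decline of 1. With 20 patients that is costly, because the main product of a pilot is an estimate of how far the score moves and how much it varies. The objective asks whether symptoms improve, and the mean within-patient change answers that more precisely than the share of patients who cross a threshold.

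The rest of the plan does not make up for this. The binary outcome has no reference rate and no test. The numeric analysis has a test, but a rank sum test needs two groups. As written, neither outcome has a usable inferential analysis, and two sections disagree on which comparison is primary.

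**Working it through.** **The plan's own figure.** The 20 patients cannot be reproduced from anything in the documents. No SD, expected change, responder rate, null rate or power is given. Every SD, mean change and responder share below is therefore an assumption.

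**Step 1: information lost by the cut.** For a normally distributed change assessed once, the efficiency of the responder proportion relative to the mean is φ(z)² / [p(1 − p)]. Here p is the responder share, z the matching normal quantile and φ the normal density.

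| Responder share | Efficiency | Loss | 20 patients act like |
|---|---|---|---|
| 50% | 0.637 | 36.3% | 12.7 |
| 40% or 60% | 0.622 | 37.8% | 12.4 |
| 35% or 65% | 0.603 | 39.7% | 12.1 |
| 30% or 70% | 0.576 | 42.4% | 11.5 |
| 20% or 80% | 0.490 | 51.0% | 9.8 |

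At 50%, for example, 0.3989² / 0.25 = 0.637. The loss equals 40% at a share of about 34% and, by symmetry, about 66%.

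For mean declines of 0.3 to 1.0 and SDs of 0.9 to 1.3, with z = (1 − mean)/SD, efficiency runs from 0.51 (mean 0.3, SD 0.9) to 0.64 (mean 1.0). That is a loss of 36% to 49%.

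**Step 2: dependence on shape.** For logistic-shaped changes cut at the median, efficiency is 4 × (1/4)² × π²/3 = 0.82, a loss of about 18%. For a uniform shape it is 4 × 1/12 = 0.33, a loss of about 67%. The 36% minimum thus belongs to the normal case.

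**Step 3: power in one illustrative case.** Assume a reference mean decline of 0.5, a treated mean decline of 1.2 and SD 1.1.
- Responder rates: 1 − Φ(0.5/1.1) = 32.5% and 1 − Φ(−0.2/1.1) = 57.2%.
- Noncentrality of the t-test on the change: (0.7/1.1) × √20 = 2.85, with 19 degrees of freedom.
- The exact binomial test cannot reach one-sided 0.025 exactly, so the two tests are compared at each size that it can attain:

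| Responders needed | One-sided size | Power, responder test | Power, t-test at the same size |
|---|---|---|---|
| 12 of 20 | 0.010 | 49% | 63% |
| 11 of 20 | 0.031 | 67% | 80% |

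The unrounded differences are 13.5 and 13.4 points.

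**Step 4: precision of the planned primary.** If 10 of 20 respond, the exact 95% interval is 27% to 73%.

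**Step 5: the any-time reading.** Steps 1 and 3 assume one assessment. The Statistical analysis wording can be read as counting a qualifying decline at any time on treatment. With no true mean change, SD 1 and correlation 0.6 between assessments (assumed), simulation puts the responder share at 16% with one assessment, 24% with two and 45% with eight. Without a named time point, the rate that no effect would produce is not fixed.

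**The case against.** A responder primary with numeric change beside it is a legitimate choice for an open-label pilot with no power target. It is easy to interpret, and the plan says explicitly that patients without a recorded decline count as failures. The only P-values described are for numeric changes, so the intended inference already rests on the score. All of that is fair, and it limits the point to which outcome is primary and how the numeric one is analysed. It does not rescue the numeric analysis, because the rank sum comparison needs a second group and none is listed.

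A reader might infer four stronger things that the documents do not support:
- That 40% or more of the information is always lost. The minimum under normality is 36%, and the documents give no responder share that would place the trial beyond 40%.
- That power falls from 77% to 49% in the example of Step 3. The 77% is the t-test at one-sided 0.025 and the 49% is the binomial test at 0.010. About half of that gap is discreteness of the exact test.
- That the numeric information is discarded, or that no SD will be available for the next trial. Mean and median changes are planned and the scores are collected, so an SD can be computed. The plan simply does not call for it.
- That the total GCSI runs from 0 to 5. That range is stated per item in the PAGI-SYM description. Whether the total is a mean or a sum of the nine items is not stated, and the meaning of a 1-point cut depends on it.

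**Conclusion.** The point holds in a limited form. The sole primary outcome is a dichotomised score with no null rate and no test, in a 20-patient study with one listed group. If changes are roughly normal, at least about 36% of the information in the mean change is lost to the primary outcome, so 20 patients act like at most about 13. The power cost in the illustrative case is about 13 points at matched size. These sizes rest on an assumed shape, SD and mean change and on a single assessment; heavier tails would reduce them.

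What does not rest on assumptions is the text itself. The numeric analysis is specified as a between-group test that one group cannot support, and the comparison labelled primary under Sample size justification is a score comparison that does not match the binary outcome.

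**What to change.** Make the primary outcome the within-patient change in total GCSI from the baseline week to week 8. Take it from the daily diary, as the objective does, and state how the total is scored and how nightly entries are averaged. Report mean and median change with the SD and a 95% confidence interval, and replace the rank sum test with a paired t or signed-rank test. Reconcile the primary comparison under Sample size justification with this outcome.

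Keep the 1-point responder proportion as a supportive outcome, with an exact interval, a named time point and dropouts counted as not improved.

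No new data, visits or patients are needed: the visit descriptions already provide a week of diary at screening and diary collection at week 8. The cost is more than a change of label. The headline becomes a score change instead of a percentage improved. Missing week 8 scores need a stated method, because counting them as failures does not carry over to a mean. The synopsis also refers both to 8 weeks of treatment and to a 12-week course; those statements must be reconciled so that the primary time point is unambiguous.
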